**Research design**

[figure not shown]
Screening and familiarisation visit including the 'Screening questionnaire pack', and test familiarisation of executive function flanker task and muscle strength test battery

2 experimental sessions i) Phase 1 and ii) Phase 4

Retiring by 23:00 the night before testing and waking at 06:00 h the day of testing

**Experimental protocol**

**Key:**

= wake up	= cognitive tests and closed-eye EEG
= Questionnaires	= warm up
= Bloods for hormone panel	= strength test battery
= intra-aural temperature	

Figure 1: Schematic of research design and experimental protocol

On arrival at 07:00 h participants will have several measures taken before being seated for an acclimatisation period. Participants height and weight will be taken using bioelectrical impedance scales (DC-430P/Tanita/Tokyo, Japan). Participants will then be seated at a desk surrounded by a screen which is required to help reduce external stimuli which could later affect the cognitive element of the study. A heart rate monitor (H10/Polar/Kempele, Finland) will be fitted around the participants chest to measure heart rate (HR) and heart rate variability (HRV) throughout the acclimatisation period. Participants will then remain seated for a 30 min acclimatisation period to reduce any transient influences of the pre-laboratory environment which could affect core body temperature reading.

During this 30-min acclimatisation period, participants would complete the '**test day questionnaire**' containing four sections; 'Section A: menstrual symptoms', 'Section B: sleep quality' 'Section C: Profile of Mood states' (Terry *et al.*, 1999) and 'Section D: caffeine withdrawal questionnaire'.

**Section A** will ask participants to categorise several menstrual symptoms with a number from 0-4 with 0 being not present and 4 being extremely present.

**Section B** will assess the participants quality of sleep over the past month and of the night before test day compared to their 'normal'.

**Section C** contains 32 feelings that people experience frequently and asks the participant to circle a number 0-4 for each feeling, with 0 being 'not at all' and 4 being 'extremely'.

**Section D** asks participants to circle a number 0-4 for each feeling listed which related to caffeine withdrawal, having not consumed caffeine for 24 h.

**Section E** will ask participants to draw a line along a number scale to indicate how tired/alert they feel. These questionnaires should take 5-10 minutes for the participant to complete.

After the completion of questionnaires, participants will have the **EEG** system fitted. Using the Enobio 8 EEG system (Neuroelectrics/Cambridge/MA), neural activity at resting-state will be measured. The silver-silver chloride (Ag|AgCl) electrodes are prepositioned (Cz, F3, F4, Pz, P7, P8, O1 and O2) according to the international 10-20 montage system (figure 2) in a head cap that is placed on the participants head prior to recording, with adjustments made after correct placement of Cz electrode. The reference electrode will be placed on the right earlobe (A2) with a small volume of gel as recommended by the manufacturer. Participants will relax for 2 min and ear plugs will be given, and they will be asked to close their eyes to reduce the level of external stimuli. After 2 min relaxation, participants will be told that the EEG recording is about to happen. Firstly, for a period of 5 min, participants will sit with their eyes closed whilst EEG is recorded (resting eyes closed [REC]). Then participants will be asked to open their eyes and focus on a black cross displayed on a computer screen in front of them, this will happen for another 5 min (resting eyes open [REO]). Participants will then be asked several temporal questions which focus on their perception of time, the questions will ask about the amount of time the participants spent with their eyes closed/open and if these times vary between TOD and phase.

[figure not shown]

Figure 2: EEG electrode placement

Following this, participants will be instructed to carry out an **executive function test battery**. The test carried out will be a modified version of Eriksen's original Flanker task (Eriksen and Eriksen, 1974; Koch and Krenn, 2021). The Flanker task is used as a measure of inhibition and cognitive flexibility; asking participants to respond to a visual stimulus depending on what is displayed on the screen and the instructions given. This modified flanker task uses arrows displayed on a screen and asking participants to focus on the central arrow that is flanked by arrows to its left and right, these flanking arrows are either congruent or incongruent to the central arrow. This test battery consists of two sections:

**Section 1** requires the participants to react to the middle arrow by pressing C on an electronic keyboard if the arrow was facing to the left and press M if it was facing to the right – measuring simple reaction time.

**Section 2** measures cognitive flexibility – this section requires participants to switch their reaction response depending on the colour of the arrows. If the middle arrow appears red, they must press C if it is pointing right and M if it is pointing to the left. If the middle arrow is green, they must treat them as in the previous section, pressing C for left facing and M for right facing. (Koch and Krenn, 2021).

Reaction time and number of correct answers for congruent and incongruent sequences (arrows in the same or different directions) would be determined and analysed as an indicator of cognitive flexibility and inhibition (two measures of executive function).

After the 30-min acclimatisation period, participants intra-aural **temperature** will be measured; two measures will be taken 2 minutes apart, if the difference between the values is  $>0.2^{\circ}\text{C}$  then a third measure would be taken. Intra-aural temperature will be measured using a tympanic thermometer (TH889J/Radiant Innovation/Hsinchu, Taiwan). The average temperature would be calculated as the mean of the closest pair of measurements (Reilly *et al.*, 2007, Edwards *et al.*, 2005). The rectal probe is the gold standard measure of core body temperature however after discussions with a group of female athletes, the decision to measure core body temperature using intra-aural was made, as it was concluded that the rectal probe would reduce participant willingness to volunteer for the study.

Commented [CG4]: need blood pressure too

**Blood pressure (BP)** will be measured as a cross-validation method of circadian rhythm using an automatic blood pressure monitor (M3 Comfort/Omron/Kyoto, Japan). Participants will remain seated with their feet flat to the floor and arm relaxed on the desk in front of them for the measure of BP.

Venipuncture of the arm would then be performed to draw blood from the participants. The blood samples would be collected in several vacutainers (gold topped for Oestrogen, progesterone and hsCRP, and purple top for inflammatory markers) with a small volume extracted and placed on ProWipes pads where the participant's blood can be drawn up in a capillary tube for **glucose and lactate** analysis using a blood analyser (Biosen C-Line GP+/EKF/Barleben, Germany). This measure will only be performed at the morning visit to consider blood glucose and lactate levels after the overnight fast. The remaining **blood samples** collected in vacutainers would be stored at -80°C before carrying out various assays, according to manufacturer's guidelines, to measure progesterone (P), oestradiol (E2) and Interleukin (IL-6), Tumour necrosis factor (TNF $\alpha$ ) and high sensitivity C reactive protein (hsCRP). Blood analysis of progesterone and oestrogen would be carried out in duplicate using commercially available serum and plasma enzyme linked immunosorbent assays (ELISA). The blood analysis would act to confirm correct phase identification during testing, with the exclusion of participants occurring after testing due to E2 or P levels not matching those defined for Phase 1 and 4 above.

*Table 1: summary table of proteins measured, their biofluid and the purpose of the measurement*

	Biofluid	Assay	Purpose of measure
Progesterone	Serum	ELISA	As a confirmation of phase of participant's cycle.
Oestradiol	Serum	ELISA	As a confirmation of phase of participant's cycle.
Luteinising hormone	Urine	Easy@Home, Easy Healthcare Corporation, IL, USA	Carried out 5 days prior to expected the LH surge which occurs 24-48 hours prior to ovulation to determine when ovulation will fall.
IL-6	Serum and Plasma	LEGENDplex Human inflammation panel 1	To measure key inflammatory markers to determine a possible relationship between inflammation and the menstrual cycle/time-of-day, resulting in possible discrepancies in strength and cognitive measures.
TNF- $\alpha$	Serum and plasma	LEGENDplex Human inflammation panel 1	To measure key inflammatory markers to determine a possible relationship between inflammation and the menstrual cycle/time-of-day, resulting in possible discrepancies in strength and cognitive measures.
hsCRP	Serum and plasma	ELISA	To measure key inflammatory markers to determine a possible relationship between inflammation and the menstrual cycle/time-of-day, resulting in possible discrepancies in strength and cognitive measures.

Following a 5-min warm up on a static bike at 80-120 watts, the participants would complete the **strength test battery** section of the study. The handgrip dynamometer measures voluntary isometric grip force (N) of the hand flexors, which is known as handgrip strength (HGS) (McGrath *et al.*, 2022). Participants would be seated on a chair with a straight back with their shoulder adducted and neutrally rotated, elbow flexed to 90° with a neutral forearm and wrist, in accordance with the American Society of Hand Therapists'. Participants would grip the dynamometer with their whole hand at the

predetermined handle position, set at the familiarisation visit, they will be asked to maximally squeeze the dynamometer for 3-seconds. 3 repeats will be carried out with the participants dominant hand, with 1-min of rest between each, recording the maximal values to determine both peak and mean values, along with height as these have shown to strongly correlate with HGS (Fiebert *et al.*, 1998).

Following this, participants would perform both countermovement (CMJ) and squat jumps (SJ), measuring flight time (s) and vertical jump height (cm). The Jump height meter (Optojump/Microgate/Bolzano, Italy) consists of two parallel bars (one receiver and one transmitter bar) that are positioned approximately 1m apart on the floor, with the athlete stood with their feet running parallel between the two bars. For SJ, participants start in an upright position with their hands on their hips, lowering into a squat position with their knees at approximately 90°, and holding this position until the researcher counts them down. On the count of 3 the participant was instructed to jump as high as they could from the predetermined squat position, keeping their hands on their hips. For CMJ, participants also begin with their hands on their hips, in the upright position. On the count of 3, they are encouraged to assume a similar squat position (knees at approximately 90°) as in the SJ as quickly as possible, jumping as high as possible immediately after. For both SJ and CMJ, participants are asked to take-off with extended knees and ankles, and land in a similar way, bending their knees as they land. Each jump type will be repeated 3 times with a rest interval of 30-seconds between each jump repetition and a 2-minute rest interval between jump types.

Participants will then carry out lower limb strength testing using the **Biodex system** (S3/Biodex/New York, U.S.A.) on their dominant leg. Seating position would be predetermined in the familiarisation visit and participants would be strapped to the chair as seen in. Participant's exact range of motion and limb weight will be determined for each visit before carrying out maximal isometric Voluntary contraction of knee extensors and flexors measured over 4s at 60° flexion. Between away and towards contractions, participants will have 30-sec and between each set, participants will have 3-min passive recovery.

**Commented [CG5]:** Flexibility would be good to measure here too

IKD dynamometry (torque-angle) with EMG confirmation?

Goniometry for something cheap and quick but above more physiological

**Commented [AS6R5]:** I'm a little confused by this comment - what do you mean? Have the changes to detail answered this question? What do you mean by flexibility?

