## Protocol

This study aims to investigate the effects of time-of-day and menstrual cycle phase on tier 2 female's cognitive and strength performance through several measures. The independent variables for this study are (i) time-of-day (three levels: 07:00, 12:00, and 18:00 h) and (ii) menstrual cycles phase in eumenorrheic females (two levels: low levels of progesterone (phase 1) and high levels of progesterone (phase 4) ( $>16\text{nmol L}^{-1}$ ; Verhagen *et al.*, 2025)). The dependent variables of this study include muscle strength, measured across three domains (maximal handgrip strength, flight time and height performing CMJ and SJ, and maximal lower limb strength), and executive function using a modified version of Eriksen's original Flanker task, (Koch and Krenn, 2021), and electroencephalography (EEG) alpha wave activity, measured with an Enobio 8 EEG system (Neuroelectrics/Cambridge/MA). Each measure will have at least one cross validation measure, to ensure greater validity in our findings.

An a-priori analysis was conducted using G\*Power version 3.1.9.6 for this study (Faul *et al.* 2007); chosen due to the intention to analyse the data using a MANOVA repeated measures within factors statistical test. The sample size for this study was determined based on a medium effect size ( $f=0.25$ ), using a statistical power of 80% and an alpha value of 0.05. This study involves one group (tier 2 females partaking in sports) with two independent variables of time of day (07:00, 12:00, and 18:00 h) and menstrual cycle phase (highest and lowest levels of progesterone). G\*Power indicated a minimum sample size of 24, however, to account for any potential data loss or dropouts, this study will aim to collect data from 30 participants.

Participants will be recruited via opportunity sampling with the use of posters placed around Lancaster University campus, online advertisements on social media platforms and through word of mouth. For individuals to participate, they must meet the extensive eligibility criteria to ensure that this study tests the effects of time-of-day and menstrual cycle phases on tier 2 female cognitive and strength performance. Participants must fit the following criteria:

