Participants will be provided with five Luteinising hormone (LH) ovulation strips (Easy@Home, Easy Healthcare Corporation, IL, USA) to take home and use three to four days prior to expected ovulation date (known by self-tracking of their menstrual cycle). These strips require participants to urinate onto the strip and wait 2-3 minutes (min) for the indicator to appear. For a positive test, the indicator line must show up darker than the control line. LH is always present in the body however there is a rise in

**Commented [CG1]:** Re screening - at the screening visit I'd suggest you ask [name] to have a look at the participant's veins.

Some young females can be very tricky to get blood from. It doesn't mean we need to exclude but might be worth having extra help in the lab - we need to be confident we're getting blood from anyone who participates...

**Commented [CG2]:** I would insert a table here or where appropriate that says (i) what we're going to measure and (ii) in what biofluid and (iii) why

e.g. Oestrogen (E2) in blood at morning visit of visit 1 and 2 to distinguish follicular vs luteal phase

Progesterone - blood

LH - urine?

FSH?

LH levels 12-36 h prior to ovulation and therefore the positive test on the strip is an indicator of when ovulation will occur for the participant. If a participant does not get a positive test, they will be sent the debrief sheet and will no longer be able to partake in the study as some females do not ovulate (anovulation/ oligo-ovulation) and therefore are not eumenorrheic (Mihm *et al.*, 2011). Participants in this study will follow a similar structure to the best practice highlighted by Verhagen *et al.*, (2025) in which one cycle of the following is required: self-reporting the onset of menses to schedule phase 1 testing, a day 1,2,3 or 4 blood sample for the determination of  $\beta$ -oestradiol and progesterone to confirm phase 1, daily LH urine sticks from 5 days before estimated day of ovulation until the LH surge to schedule phase 2 testing, and a blood sample for the determination of progesterone ( $\geq 16 \text{ nmol.L}^{-1}$ ) +7 days ( $\pm 1$ ) days after confirmation of the LH surge to confirm phase 4 testing.

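### Does the post-testing hormone exclusion need numeric Phase 1 and oestradiol limits in the protocol before it can be trusted?

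*Protocol*

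**What the plan says.** Three parts of the protocol bear on this.

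- The opening section defines the phase factor by progesterone alone: low in Phase 1, and high in Phase 4, with a limit of more than 16 nmol/L.
- The phase-verification text (after the description of the LH strips) requires a blood sample within the first four days of the cycle, with "oestradiol and progesterone to confirm phase 1". For Phase 4 it requires "a blood sample for the determination of progesterone" of at least 16 nmol/L, taken 7 days (plus or minus 1) after the LH surge. A woman with no positive LH test leaves the study.
- The blood-sampling text under the experimental protocol says samples are "stored at -80°C before carrying out various assays". It then uses the results to confirm phase, "with the exclusion of participants occurring after testing due to" oestradiol or progesterone "levels not matching those defined for Phase 1 and 4 above". Table 1 gives the purpose of both hormones as "As a confirmation of phase of" the participant's cycle, with no limit for either.

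**The concern.** The exclusion rule points back to levels that are mostly not there. A reader who follows the pointer finds one number, for Phase 4 progesterone. It is also unclear whether oestradiol counts in Phase 4: the verification text names only progesterone there, while the blood-sampling text attaches both hormones to both phases.

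Menstrual phase is one of the two study factors, and the rule is applied once performance data exist. If limits were chosen at that stage, two people could exclude different women. In the worst case a limit could be picked because it gave a favourable phase contrast, so both reproducibility and the false-positive rate would be at stake.

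**Working it through.** **1. Which limits are given.**

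| Check | Timing anchor | Numeric limit |
|---|---|---|
| Phase 1 progesterone | First four days after reported menses onset | None; described as low |
| Phase 1 oestradiol | Same | None |
| Phase 4 progesterone | 7 ± 1 days after a positive LH test | 16 nmol/L (strict in the opening section, non-strict in the verification text) |
| Phase 4 oestradiol | Same | None; not named in the verification text |

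On the verification text, two of three checks lack a number. On the wider reading of the exclusion sentence, three of four do. The textual observation is correct.

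**2. What the missing limits decide.** Every visit is placed in a phase by timing before any assay is read. The hormone check acts only on women already timed as in phase. The factor is defined by progesterone, and its high level has a number. The open limits therefore affect only women whose timed Phase 1 visit, or whose oestradiol, looks out of place. The protocol gives no figure for how many that would be.

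**3. The plan's own margin for losses.** The stated minimum of 24 is reproduced by a one-group repeated-measures MANOVA with f = 0.25, m = 6 cells (3 times × 2 phases) and an assumed correlation of 0.5:

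- noncentrality = f² × m × N / (1 − ρ) = 0.0625 × 6 × 24 / 0.5 = 18
- degrees of freedom 5 and 24 − 6 + 1 = 19
- power 0.825

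The target of 30 leaves 30 − 24 = 6 women, or 20%, for all losses together.

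**4. How much harm open limits could do.** Simulation: N = 30, null paired phase difference, two-sided t test at 0.05, hormone rank unrelated to outcome, two hormones independent, 200,000 runs. The analyst is assumed to try every available limit and keep the smallest p-value.

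| Women each limit can remove | One open limit | Two open limits |
|---|---|---|
| 0 or 1 | 0.059 | 0.068 |
| 0, 1 or 2 | 0.065 | 0.084 |
| 0, 3 or 6 | 0.078 | 0.119 |
| One limit per hormone, set without regard to outcomes | 0.050 | 0.050 |

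The last row is what sensible practice delivers, whatever the limit and even if it is written down late. The 0.119 needs two limits that together may remove up to 6 + 6 = 12 of 30 women. That leaves as few as 18, below the plan's minimum of 24, and it takes the best of 3 × 3 = 9 analyses.

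**5. Would keeping the verified day help?** One could drop only the unverified phase and fit a mixed model. A woman with one phase adds nothing to a within-woman phase contrast. For 07:00 versus 18:00, let k women have one verified phase, and let r be the correlation between a woman's time differences in the two phases. The information is 2(30 − k)/(1 + r) without these women, and k more with them.

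- k = 3, r = 0: √(54/57) = 0.973, so the standard error falls by 2.7%.
- k = 6, r = 0.5: √(32/38) = 0.918, so it falls by 8.2%.

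Both k and r are assumed. The gain is small.

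**The case for a change.** The strongest argument for a change is that the protocol does not defer these limits to another document. It says they are already defined in its own text, and they are not. The published best practice it cites is followed only in structure, which does not amount to adopting that source's limits, and the exclusion sentence does not refer to it. The one number that is written out makes the absence of the others more noticeable. Good faith alone does not make two analysts agree.

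The part about the text stands: the cross-reference is loose, and the role of oestradiol in Phase 4 is not settled by the words. The inference to bias does not. Freezing samples and assaying them later is normal and does not show that outcomes will be inspected first; the protocol nowhere says they will be. Nor can the rule as a whole be called inoperable, because the Phase 4 progesterone check has its number. Who applies the limits and whether all tested women are analysed as a sensitivity check are matters usually settled in a statistical analysis plan, which may exist but is not at hand.

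**Conclusion.** No change to the plan follows. This is a gap in detail with a loose back-reference, and analysts will fill it sensibly. Phase is set first by menses onset and the LH test, the hormone that defines the factor has a limit where it must be high, and ordinary laboratory limits for the rest leave the phase contrast valid at 0.05. The inflation to between 0.059 and 0.119 describes deliberate selection of the best p-value under assumed numbers of excluded women. No figure in the protocol supports any of those rows, so they do not measure a fault in this plan. The two inequality signs differ only for a result of exactly 16 nmol/L.

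This conclusion assumes that limits are chosen without reference to the performance results and that the timing anchors are followed as written. If there were evidence that limits had been set after the phase results were seen, the judgement would change. The protocol gives none.
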